12.5 Subject Disposition and Discontinuations

Patient disposition will be summarized for the total enrolled population and by treatment group. The following data will be presented:

- The number of patients who were screened and randomized;
- The number and proportion of patients in each analysis population;
- The number and percentage of patients who completed the study;
- The number and percentage of patients who discontinued prematurely from the study and the associated reasons:
- The number and percentage of patients who attended each follow-up visit.

12.6 Baseline and Demographic Characteristics

Demographic and baseline data will be summarized by treatment group using descriptive statistics. Demographics will include, among others, age, gender, ethnicity, weight, height, body mass index. Protocol deviations/violations will be provided as a patient data listing only. Major protocol deviations/ violations will be identified and their impact rated for analysis purposes.

The demographics and baseline characteristics summary will be presented for the ITT and the PP populations to allow review of the characteristics of those included in the efficacy analyses, which will be based on these analysis sets.

12.6.1 Prior and Concomitant Medications

Medications used in this study will be coded by using the World Health Organization Drug Dictionary Enhanced and categorized as the following:

- Prior medication: Any medication that started before the first dose of study drug, independently of when it ended.
- Concomitant medication: Medication continued or newly received at or after first dose of study drug to the follow-up on Day 45 or earlier if early-terminated.

• Post-treatment medication: not applicable.

A given medication can be classified using the above, in one or more categories. If a medication has a missing or partial missing start/end date or time and cannot be determined whether was taken before the first dose of study drug, or concomitantly, it will be considered as prior and concomitant. Prior medications and concomitant medications will be summarized descriptively based on the ITT population.

12.6.2 Study Drug Exposure

The duration of study drug exposure is defined as follows: Last dose date minus first dose date plus 1 day, regardless of any interruptions in dosing. If the last dose date of study drug is missing, the patient's discontinuation or completion date will be used for analysis purpose. Duration of study drug exposure will be summarized descriptively as a continuous variable (number, mean, SD, median, minimum, and maximum), by study group, using the safety population subset of the ITT population.

12.6.3 Study Drug Compliance

Study drug compliance will be performed on the Safety population. Study drug compliance will be assessed by calculating as follows: $100 \times (1 - [\text{total number of days of study drug interruption}]/(\text{duration of study drug exposure}))$. The total number of days of study drug interruption is defined as the sum of (number of days of each study drug interruption is defined as the interruption end date minus the corresponding interruption start date plus 1 day. Treatment compliance percentages will be summarized descriptively as continuous variables (number, mean, SD, median, minimum, and maximum). The percentage of patients whose compliance is <80% or $\ge80\%$ will be summarized, by study group.

12.7 Efficacy Analysis

12.7.1 Analysis of Primary Endpoint

The proportion of patients requiring mechanical ventilation (includes ECMO) AND/OR deceased by Day 60 will be analyzed using a Chi-Square test (or a Fisher exact test if the expected values in any of the cells of the contingency table are below 5).

Logistic regression including treatment group, age group and other prognostic factors at baseline will also be performed.

Missing observations will be treated as a non-response (i.e. patient not considered as alive and free of respiratory failure) for the primary analyses on ITT. Sensitivity analyses where missing observations will be imputed using different methods will also be performed and will be further detailed in the SAP.

Additional post-hoc analyses may be performed in an exploratory manner depending on the frequency of other phenotypes or concomitant drugs.

Full details will be specified in the SAP and its Addendum dedicated to the study expansion.

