In the Phase 3 extension of the study, the overall design remains unchanged and so is the main efficacy variable, the Health Status score. Based on sample size calculation using the effect size observed in the pilot portion of the study for the revised Primary Efficacy Endpoint in the subset of patients with a Health Status score 3 or 4 at baseline and an alpha of 0.05, approximately 264 additional patients with Health Status score 3 or 4 at baseline will be recruited and randomized for the treatment phase of the study. Patients will be enrolled at approximately 25-30 centers in the United States of America and in Canada.

To ensure the study extension is powered adequately and self-sufficient to be confirmatory, an interim sample size re-estimation including a futility analysis will occur once 42% (112) of the 264 planned patients have either completed the Day 60 primary endpoint assessment or terminated their study participation early. A maximum of 462 patients total may be enrolled, dependent upon the results of the interim sample size reestimation.

Below is a schematic of the study structure for Health Status 3 + 4 patients in the Phase 2 pilot and the Phase 3 extension:

Study Design Overview (cont'd)

Adult male and female patients 18 years and older, exhibiting a symptomatology typical of COVID-19 disease, confirmed to be positive for SARS-CoV-2 and under observation/admitted in the hospital for preventative reasons, will be offered to participate in this interventional study. There is no time limit between the onset of symptoms or the COVID positivity prior to the screening in the expansion of the study.

If agreeable, patients will be consented and eligibility will be confirmed. Eligible patients will be randomized (1:1) to receive in a blinded fashion, either LAU-7b 300 mg per day (3 capsules of 100 mg each), once a day for 3 days, or a matching placebo administered in the same fashion (the "Initial Treatment").

Patients will continue the treatment with LAU-7b 200 mg per day (2 capsules of 100 mg each), once a day for the remaining 11 days, or a matching placebo administered in the same fashion, on top of SOC (the "Follow-up Treatment").

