Using the proportion of patients requiring mechanical ventilation AND/OR deceased by Day 60 in the pilot portion of the study, an effect size of 7% change (i.e. 7% in the control group vs. 0% in the investigational group), comparing the active arm versus the control (placebo) arm, and a minimum of 90% statistical power of detecting a difference of 7% using a two-tailed Fisher Exact test, with a nominal alpha of 0.05, a total sample size of 264 patients (132 per arm) with a Heath Status score of 3 or 4 at baseline is required for the Phase 3 confirmatory portion of this study.

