12.7.2 Analysis of Secondary Efficacy Endpoints

Pre-defined Clinical Parameters:

- The ordinal scale will be used to estimate a proportional odds model. The primary hypothesis test will be based on a test of whether the common odds ratio for treatment is equal to one. The model fit using a goodness-of-fit likelihood ratio test will be evaluated. The distribution of severity results will be summarized by treatment arm as percentages. The validity of the proportionality assumption will be evaluated and tested. Participants without final outcome data will be excluded from the analysis. Sensitivity analyses will evaluate the impact of making different assumptions about missing observations. These sensitivity analyses will be fully defined in the SAP.
- Count data variables: The number of days of hospitalization, the number of days in ICU, the number of days under mechanical ventilation...etc., will be tabulated by treatment and compared with an appropriate count data model, e.g., ANOVA model (if assumptions of normality and homogeneity of variance appear acceptable), Poisson regression, negative binomial regression, zero-inflated regression, etc., depending on their distribution.
- Time to event data variables: The time to mechanical ventilation, time to recovery, time to aggravation (worsening by one category on the ordinal scale), and time to death will be tabulated by treatment and compared using a Cox proportional hazards model. If the proportional hazards assumption is violated, a stratified analysis will be conducted using stratified Cox regression. Additionally, Kaplan-Meier methods will be used to produce graphical presentations of the survival (aggravation-free survival, survival) by treatment group and to estimate cumulative aggravation-free survival and survival rates by treatment group.
- Change in ordinal scale at specific time points will be summarized by proportions (e.g., proportion who have a 1-, 2-, 3-, or 4-point improvement or 1-, 2-, 3-, 4-point worsening).
- Mean change-from-baseline for the ordinal scale will be analyzed through time, using a mixed model repeated measure (MMRM) model.
- Body weight and BMI changes from screening will be summarized using descriptive statistics by treatment and compared between treatments using an analysis of covariance (ANCOVA) with treatment as fixed effect; and adjustment for screening Ordinal Scale Health Status, and weight or BMI at baseline as covariates.

Formal Futility Analysis (Pilot Portion):

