The primary analysis for the primary endpoint will treat missing observations as is without any imputation, i.e. Including all patients with available health status/survival data at Day 60 for the primary analysis. This is the complete case analysis.

The results from this approach will be presented as the primary analysis in the CSR, while the original analysis using the imputation method specified in the protocol and the SAP will still be included in the CSR, but referred to as the "former planned primary analysis".

3. Additional Analyses

The updated imputation method is defined as follows:

- For the primary analyses on the intent-to-treat (ITT) population, missing observations will not be imputed.
- The original method, which assigned missing observations to non-response (health status 6-7), will continue to be reported as part of the CSR to ensure full transparency.
- The sensitivity and supplementary analyses will remain the same.
- The table numbering follows the ICH E3 guideline for CSR. Since both the pilot study and the extension study are included in the CSR, along with the additional tables described in this SAP addendum, the numbering rule is described as follows:
 - o Main tables from the pilot study are numbered without any suffix.
 - Main tables from the extension study are numbered with the suffix "e".
 - Additional tables described in this SAP addendum are numbered with ".1e" replacing the suffix "e".
- The impacted tables to be differentiated from the main tables in the extension study are listed below:
 - Table 14.2.1.1.1e Primary Analysis: Proportion of Patients Requiring Mechanical Ventilation (includes ECMO) and/or Deceased by Day 60 – ITT;
 - Table 14.2.1.4.1e Supplemental Analysis: Proportion of Patients Requiring Mechanical Ventilation (includes ECMO) and/or Deceased by Day 60 Analyzed by Logistic Regression;
 - Table 14.2.3.1.1e Proportion of Patients Alive and Free of Respiratory Failure on Day 29 ITT;
 - Table 14.2.3.2.1e Proportion of Patients Alive and Free of Respiratory Failure on Day 29 PP;

Status: Version 1.0

Protocol Number: LAU-20-01

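### With no LAU-7b events, the case the trial is sized on, the planned logistic and Cox models give no finite treatment effect and uninformative Wald results, and the supplied text names no fallback

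*Protocol*

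**What the plan says.** Protocol 12.1 sizes the Phase 3 extension at 132 per arm for at least 90% power, assuming "7% in the control group vs. 0% in the investigational group" and "using a two-tailed Fisher Exact test, with a nominal alpha of 0.05". Protocol 12.2 ties the maximum size of 231 per arm to 4% v 0%, so LAU-7b is again assumed to have no events. Protocol 5.4.2.1 reports the pilot patients with Health Status 3 or 4: no deaths or ventilations among 76 on LAU-7b, and 5 of 72 ventilated on placebo.

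Protocol 12.7.1 makes chi-square the primary test, or Fisher's exact test if any expected cell count is below 5. It then adds: "Logistic regression including treatment group, age group and other prognostic factors at baseline will also be performed". Missing outcomes count as events in the primary ITT analysis. Protocol 12.7.2 has time to ventilation, recovery, aggravation and death "compared using a Cox proportional hazards model", with a stratified Cox model if hazards are not proportional. Kaplan-Meier methods are for graphs and cumulative rates, and no log-rank test is named.

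The SAP Addendum (section 2) changes the primary analysis to complete cases. Section 3 lists Table 14.2.1.4.1e among the affected tables: "Supplemental Analysis: Proportion of Patients Requiring Mechanical Ventilation (includes ECMO) and/or Deceased by Day 60 Analyzed by Logistic Regression". None of this text states an estimator, a type of test (Wald, likelihood-ratio or score) or a rule for an arm with no events. Protocol 12.7.1 leaves full details to the SAP and its addendum. The SAP of 29SEP2023 is not among the supplied documents.

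**The concern.** An arm with no events separates the data. The logistic likelihood keeps rising as the treatment coefficient goes to minus infinity, and the Cox partial likelihood does the same. Software then prints whatever coefficient it had reached when it stopped, with a very large standard error, a Wald p-value near 1 and an interval that is in effect unbounded.

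This is the scenario the plan assumes, so it needs a stated method. Protocol 12.7.1 names no other covariate-adjusted model for the primary endpoint. An odds ratio near zero with p near 1, printed beside a significant Fisher result, would look like a contradiction although it is only an artefact. The hazard ratios for ventilation and death would be equally unusable.

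**Working it through.** **Inputs.** Rates, arm size and test come from Protocol 12.1, the maximum size from 12.2, and the pilot counts from 5.4.2.1. The following are assumptions made for this check: the alternative LAU-7b event rates, the missing-data rates, the covariate data in step 4, and, for Cox, nine placebo events at distinct times with nobody censored before the last.

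**1. The plan's own figures.** With 0 events on LAU-7b and 132 per arm, two-sided Fisher gives p=0.060 for 5 placebo events and p=0.029 for 6. Power is therefore P(X ≥ 6), X ~ Binomial(132, 0.07), which is 90.6%. At 231 per arm and 4% v 0%, power is 90.3%. The pilot 5/72 v 0/76 gives Fisher p=0.025, as stated. All three reproduce.

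**2. How likely an empty cell is.** P(no LAU-7b event in 132) = (1 − p)^132. This is 100% at p=0, 52% at 0.5%, 27% at 1% and 7% at 2%.

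**3. Logistic model at the design point.** 0.07 × 132 = 9.24, so take 9/132 v 0/132. The LAU-7b contribution to the log-likelihood is −132·ln(1 + exp(α + β)), which rises towards 0 as β → −∞, so there is no maximum. Newton-Raphson lowers β by about 1 per iteration:

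| Iterations | Coefficient | SE | Wald p |
|---|---|---|---|
| 16 | −14.6 | 474 | 0.98 |
| 20 | −18.6 | 3,498 | 0.996 |
| 25 | −23.6 | 42,619 | 0.9996 |

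**4. Other inference from the same counts.**
- Expected events per arm: 9 × 132/264 = 4.5, below 5, so the protocol's rule selects Fisher: p=0.0034.
- Score test of the logistic model: 264 × 9/255 = 9.32, p=0.0023.
- Likelihood-ratio test of the logistic model: 12.79, p=0.0003.
- Firth: without covariates this adds 0.5 to each cell, so OR = (0.5 × 123.5)/(132.5 × 9.5) = 0.049; penalised likelihood-ratio p=0.0014.
- With two illustrative binary covariates: Wald p about 1, likelihood-ratio p=0.0005, score p=0.003, Firth OR 0.053 with p=0.002.

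**5. Cox model, 9 v 0 events.** The log partial likelihood rises from −50.05 at β=0 to −43.67 at β=−20 and has no maximum. At β=−20 the SE is 7,229 and Wald p=0.998. The score (log-rank) statistic is 9.28, p=0.0023. The likelihood-ratio statistic is 12.76, p=0.0004.

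**6. Effect of the missing-data rule on the logistic model.** With missing counted as an event and one missing outcome per arm, the counts are 10/132 v 1/132. Then the log OR is ln[(1 × 122)/(131 × 10)] = −2.37, SE = √(1/1 + 1/131 + 1/10 + 1/122) = 1.06, and Wald p=0.025 (Fisher 0.010). One missing LAU-7b outcome makes the estimate finite. The chance of none among 132 is 27%, 7%, 1.8% or 0.1% at missing rates of 1%, 2%, 3% or 5%. With complete cases, missing outcomes no longer fill the empty cell.

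**The case against.** A reader might infer that the models would show no effect and so contradict the primary result. The documents do not support that. They do not specify Wald tests, and likelihood-ratio and score tests of the same logistic and Cox models give p=0.0003 to 0.0023, stronger than Fisher. What fails under any choice of test is the odds or hazard ratio and its Wald interval.

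Four further objections have weight:
- The primary analysis is Fisher or chi-square. The logistic model is additional and labelled supplemental, and the Cox models serve secondary endpoints.
- Estimator and sparse-data rules are SAP-level detail, and the SAP of 29SEP2023 may contain them.
- The Addendum leaves sensitivity and supplementary analyses unchanged and numbers its tables as additions. A logistic table with missing counted as events would therefore probably remain beside Table 14.2.1.4.1e, and it would usually have a finite estimate.
- The problem is conditional. The supplied documents do not report the extension's event counts, and one observed LAU-7b event makes the unadjusted logistic estimate finite.

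These points limit the reach of the concern without removing it. Table 14.2.1.4.1e is listed as affected by the complete-case rule. The missing-as-event rule is stated for the binary primary endpoint, and Protocol 12.7.2 does not extend it to the Cox models. An empty LAU-7b cell is the plan's design case.

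**Conclusion.** The concern holds in a limited form. If LAU-7b has no events, the supplemental logistic regression of the primary endpoint and the Cox models for time to ventilation and time to death yield no finite effect estimate and uninformative Wald output. At the design point the reported logistic p-value could be anything from 0.0003 to about 1, depending on a choice of test that the supplied text does not make. The primary test is untouched.

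A reader might extend this to all the Cox analyses or call them covariate-adjusted. Protocol 12.7.2 does not describe them that way, and nothing implies zero LAU-7b events for recovery or aggravation. Nor can it be said that separation occurred, or that no remedy exists in the SAP of 29SEP2023.

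The result rests on zero LAU-7b events, on reading the Addendum's list as applying complete cases to Table 14.2.1.4.1e, and, for the Cox figures, on the assumed event times.

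**What to change.** First check the SAP of 29SEP2023 for an estimator and a zero-event rule. If it has none, state that:
- the logistic model for the primary endpoint, including Table 14.2.1.4.1e, uses Firth penalised likelihood with profile-likelihood intervals (or exact logistic regression);
- time to ventilation and time to death take their p-value from the log-rank (score) test and their hazard ratio from a Firth-penalised Cox model.

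Apply this at least whenever an arm has no events. It needs only SAP wording and a standard software option, with no new data. Firth shrinks the estimate slightly. Results were first released on 14MAR2024, so the change must be labelled post hoc unless the 29SEP2023 SAP already contains it.

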12.7.2 Analysis of Secondary Efficacy Endpoints

Pre-defined Clinical Parameters:

- The ordinal scale will be used to estimate a proportional odds model. The primary hypothesis test will be based on a test of whether the common odds ratio for treatment is equal to one. The model fit using a goodness-of-fit likelihood ratio test will be evaluated. The distribution of severity results will be summarized by treatment arm as percentages. The validity of the proportionality assumption will be evaluated and tested. Participants without final outcome data will be excluded from the analysis. Sensitivity analyses will evaluate the impact of making different assumptions about missing observations. These sensitivity analyses will be fully defined in the SAP.
- Count data variables: The number of days of hospitalization, the number of days in ICU, the number of days under mechanical ventilation...etc., will be tabulated by treatment and compared with an appropriate count data model, e.g., ANOVA model (if assumptions of normality and homogeneity of variance appear acceptable), Poisson regression, negative binomial regression, zero-inflated regression, etc., depending on their distribution.
- Time to event data variables: The time to mechanical ventilation, time to recovery, time to aggravation (worsening by one category on the ordinal scale), and time to death will be tabulated by treatment and compared using a Cox proportional hazards model. If the proportional hazards assumption is violated, a stratified analysis will be conducted using stratified Cox regression. Additionally, Kaplan-Meier methods will be used to produce graphical presentations of the survival (aggravation-free survival, survival) by treatment group and to estimate cumulative aggravation-free survival and survival rates by treatment group.
- Change in ordinal scale at specific time points will be summarized by proportions (e.g., proportion who have a 1-, 2-, 3-, or 4-point improvement or 1-, 2-, 3-, 4-point worsening).
- Mean change-from-baseline for the ordinal scale will be analyzed through time, using a mixed model repeated measure (MMRM) model.
- Body weight and BMI changes from screening will be summarized using descriptive statistics by treatment and compared between treatments using an analysis of covariance (ANCOVA) with treatment as fixed effect; and adjustment for screening Ordinal Scale Health Status, and weight or BMI at baseline as covariates.

Formal Futility Analysis (Pilot Portion):

When approximately 50 patients per arm were available for health status/efficacy data from Day 29 (actual 102 patients across the two treatment arms), a formal futility analysis based on the initial primary efficacy endpoint derived from the 7-point Ordinal Scale data was carried out and reported to the DSMB for formulation of a recommendation to the Sponsor. The aim of this futility analysis/stopping rule was to ensure that there is a high probability of stopping the study when there is a true underlying excess risk of disease deterioration with the use of the investigational product, and a low probability of stopping the study when there is no such risk.

In this study, the appropriate stopping rule was based on the proportion of patients alive and free of respiratory failure, corresponding to Ordinal Scale scores of 1 to 4 inclusively, on Day 29. The proportion of patients alive and free of respiratory failure has an expected frequency in the control arm of 78% (Kim *et al.* Error! Bookmark not defined.). The proportion of patients on the investigational product should be improved.

The rule was to stop the study if the observed investigational product rate was numerically lower than the LAU-7b for the treatment of COVID-19 disease in Adults

Amendment 5, V2.4, Aug 4th, 2023

67 of 79

observed control (placebo) arm rate. Based on Kim *et al.* Error! Bookmark not defined, assuming that the true underlying control arm (placebo) rate is 78% and using a normal approximation when comparing proportions, it is estimated that when using this rule:

the probability of stopping the study is \sim 5% if the true underlying investigational product rate is 90%. the probability of stopping the study is \sim 50% if the true underlying investigational product rate is 78% (equal to the assumed true underlying control arm rate). the probability of stopping the study is \sim 91% if the true underlying investigational product rate is 66%.

The Futility Analysis was performed and the DSMB provided their recommendation on 30Mar2021 to continue the study since the criteria for futility was not met.

Quality of Life Endpoints:

Quality-of-life data will be derived from the questionnaire according to the corresponding scoring manual and will be summarized by treatment group. Patients' health state will be derived from the EQ-5D-5L questionnaire. Data will be summarized by treatment group using descriptive statistics. Analysis of the absolute change from screening for the EQ-5D-5L will be performed using an ANCOVA with treatment as fixed effect and EQ-5D-5L score at baseline as a covariate.

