- 12. Efficacy: Time to mechanical ventilation, defined here as a move from baseline to category 6 on the ordinal scale patient status, compared between the active and control (placebo) arms of the study.
- 13. Efficacy: Time to death, defined here as a move from baseline to category 7 on the ordinal scale patient status, censored to Day 60 if it happens later than Day 60, compared between the active and control (placebo) arms of the study.
- 14. Efficacy: Duration of hospitalization (days) within the study period Days 1-60, compared between the active and control (placebo) arms of the study.
- 15. Quality-of-Life: The change from baseline to Days 14, 29, 45 and 60 in the score obtained on the EQ-5D-5L survey, a well-documented scoring system that has been widely used and validated as a QoL assessment tool, compared between the active and control (placebo) arms of the study, in patients reaching Days 14, 29, 45 and 60 and able to fill the questionnaire.

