7.2 Study Overview

7.2.1 Description

RESOLUTION is a multicentre, randomized, double-blind (patients, Investigators and blinded study staff), placebo-controlled Phase II study of LAU-7b for the treatment of COVID-19 disease in patients at a higher risk than the general COVID-19 disease population to develop complications while hospitalized.

To be eligible for the study, patients must be symptomatic of COVID-19, confirmed by PCR (or alternates but excluding rapid antigen tests)) to have a SARS-CoV-2 infection, be aged 18 years and above, and meet all other study inclusion and none of the exclusion criteria at screening. There is no time limit between the onset of symptoms or the confirmation of SARS-CoV-2 infection and screening.

Eligible patients will be randomized 1:1, at each clinical site, to either LAU-7b (active) group or placebo (control) group. After randomization, patients will enter the treatment phase of the study. There will be no active control treatment but patients will undergo the COVID-19 disease SOC at their institution.

Since the study randomizes only confirmed cases of SARS-CoV-2 infection, the screen failure rate is very low. It is estimated that based on sample size calculation using the effect size observed in the pilot portion of the study for the revised Primary Efficacy Endpoint in the subset of patients with Health Status score 3 or 4 at baseline, up to a total of approximately 264 patients with a Health Status score 3 or 4 at baseline will be recruited in the expansion. Patients will be enrolled at approximately 25-30 centers in the United States of America and in Canada. The study treatment (LAU-7b or matching placebo) will be administered once a day in the fed state (with the main meal of the day if possible) for up to 14 days on treatment.

Patients will be evaluated at pre-specified times during and after the study treatment period, for efficacy, safety, as well as for Quality of Life.

This design is appropriate for this phase of development (confirmatory Phase 3 portion) and will ensure that the highest quality of data is collected with minimal bias and the patient's safety and wellbeing are preserved. A Data and Safety Monitoring Board (DSMB) is monitoring this study.

The overall study structure for Health Status 3+4 patients in the Phase 2 pilot and the Phase 3 extension is presented below in Figure 2.

[figure not shown]

Figure 2: Overall structure of the study

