7.3.3 Randomization Scheme and Stratification

Computer-generated randomization sequences will be programmed into the IWRS. At the time of Randomization, not before, the IWRS will assign a Subject number (Randomization Number) to each patient. Randomization will be stratified by clinical site and randomized in a 1:1 double-blinded fashion to either LAU-7b (active) group or the placebo (control) group. Stratification by clinical site is appropriate when each site is expected to randomize a sizeable number of patients; this will enable an even distribution of patients among the two treatment groups, by site. Detailed instructions for randomization will be provided separately.

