12 STATISTICAL ANALYSIS

A statistical analysis plan (SAP) will provide details of the methods of analysis to address all study objectives. The SAP may be amended during the course of the study, but will be finalized before the cutoff date for any analysis, interim or final.

Data summaries by treatment group will be presented. For categorical data such as the 7-point Ordinal Scale, data will be tabulated in frequency tables to display the number and proportion of patients for each category by treatment group. For continuous variables, data will be summarized with the number of patients, mean, standard deviation, median, and minimum and maximum values by treatment group. Baseline assessments for each outcome variable will be defined as the screening measurement unless a repeat value was obtained, see restrictions in Section 9.2.1.1, before the first dose of study drug. Statistical significance will be set at the 5% level (one-sided) for the pilot portion and at the 5% level (two-sided) for the extension. Consideration

will be given for adjusting for pre-specified prognostic baseline factors such as age, the ordinal scale health status at baseline and comorbidities, where applicable.

Diligent efforts will be made to prevent missing data in the study. For example, patients who discontinue the study treatment early should still be followed for all regularly scheduled visits for safety and relevant efficacy assessments, until the Day 60 follow-up. A clear distinction should be made between treatment discontinuation and study withdrawal. Efficacy assessments occurring after treatment discontinuation should not be included in the per-protocol analysis.

Database lock and statistical analyses will be performed for the pilot portion and the extension, separately.

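### The only stated response to non-proportional hazards, stratified Cox regression, handles a non-proportional baseline covariate but not a non-proportional treatment effect

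*Protocol*

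**What the plan says.** Protocol Section 12.7.2 lists time to mechanical ventilation, recovery, aggravation and death, to be tabulated by treatment and "compared using a Cox proportional hazards model". The next sentence is the whole contingency: "If the proportional hazards assumption is violated, a stratified analysis will be conducted using stratified Cox regression". It does not say which term's proportionality is checked, by what diagnostic, or what the strata are. Separately, "Kaplan-Meier methods will be used to produce graphical presentations of the survival", with cumulative rates by arm. These are planned in addition and are not tied to a failure of the assumption.

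Candidate strata appear elsewhere. Section 7.3.3 says "Randomization will be stratified by clinical site and randomized in a 1:1 double-blinded fashion", and Section 12 says that consideration "will be given for adjusting for pre-specified prognostic baseline factors such as age", baseline health status and comorbidities.

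The SAP addendum adds no time-to-event method. It refers to a SAP dated 29SEP2023 for the full description of the analysis, and records that results were initially released on 14MAR2024. That SAP is not among the supplied documents.

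**The concern.** A stratified Cox model relaxes proportionality for the stratifying variable only. Treatment is the one comparison that Section 12.7.2 names, so it is the term whose proportionality matters most, and the stated response does not reach it. A team that follows the rule after a failed check would refit the model, obtain another single treatment hazard ratio resting on the same failed assumption, and could present it as corrected.

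A treatment effect that changes over time is plausible here: study drug is given for up to 14 days and follow-up runs to Day 60. What is at stake is how the time-to-event results are read, above all time to recovery and time to aggravation.

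**Working it through.** **1. The plan's own figures.** The documents give no hazards, hazard ratio, event count or power for any time-to-event endpoint. The only sample-size figure is 264 (132 per arm), for the primary endpoint. It reproduces: exact power of the two-sided Fisher test at 7% against 0%, alpha 0.05, is 90.6% at 132 per arm, and 131 per arm is the smallest number that reaches 90%. It is used below only as the trial's size.

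**2. What stratification does.** For stratum k and treatment x (0 or 1), the stratified Cox model is h_k(t | x) = h_0k(t) · exp(βx).
- If k is a baseline covariate, h_0k(t) is free in each stratum, but β is still one constant. If the true effect is β(t), the model is wrong in the same way as before.
- If k is treatment, x is constant within each stratum, exp(βx) cancels from the partial likelihood, and β is not estimated.

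**3. Numerical check.** From the protocol: n = 264, 1:1 allocation, and a Day 60 horizon (Section 7.1.3 has time to death "censored to Day 60 if it happens later than Day 60"). For sites, Section 7.2.1 says "Patients will be enrolled at approximately 25-30 centers in the United States of America and in Canada"; 28 were assumed. All hazards are assumptions. There were 400 replicates per scenario, and proportionality was tested at 5% by correlating Schoenfeld residuals with ranked event time.
- Scenario A: treatment hazard ratio 2.0 to Day 7, then 0.67, with a proportional binary baseline factor (hazards 0.10 and 0.05 per day).
- Scenario B: constant treatment hazard ratio 1.5, with a non-proportional baseline factor (hazards 0.20 then 0.05 per day in one level, 0.03 then 0.15 in the other, changing at Day 7).

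| Model | A: treatment HR | A: PH for treatment rejected | B: treatment HR | B: PH for treatment rejected |
|---|---|---|---|---|
| Unstratified | 1.19 | 96% | 1.46 | 6.5% |
| Stratified by baseline factor | 1.23 | 95% | 1.51 | 4% |
| Stratified by 28 sites | 1.31 | 80% | 1.45 | 2% |
| Separate HR to Day 7 / after | 2.00 / 0.68 | – | 1.52 / 1.51 | – |

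In A, stratification neither recovers the pattern nor removes the violation. The lower rejection rate with site strata reflects thin strata (264 / 28 ≈ 9 patients per site), not a better fit. In B, the covariate-adjusted model rejected proportionality for the baseline factor in 100% of runs, and stratifying on that factor gave 1.51 against a true 1.5. There the rule does its job.

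**4. Which endpoints are touched.** At the design rates for the composite of ventilation or death, expected events are 0.07 × 132 = 9.24 on placebo and 0 × 132 = 0 on LAU-7b. In the pilot subgroup (Section 5.4.2.1), none of 76 LAU-7b patients died or was ventilated, against 4 deaths and 5 ventilations among 72 on placebo. With no events in one arm the Cox estimate is not finite, so for these two endpoints sparse events are the first obstacle. Recovery and aggravation are where the rule would actually be used.

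**5. How far the illustration carries.** Scenario A changes at Day 7 and reverses direction, whereas dosing ends on Day 14. Under a second assumed set (placebo 0.10 per day; LAU-7b 0.16 to Day 7, then 0.07), ordinary Cox gave 1.05 and stratified Cox 1.06. Ignoring the baseline factor in that set, the share recovered by Day 14 is 1 − exp(−0.10 × 14) = 1 − exp(−1.4) = 75% on placebo and 1 − exp(−(0.16 × 7 + 0.07 × 7)) = 1 − exp(−1.61) = 80% on LAU-7b. With most events on treatment, an effect that merely waned after Day 14 would distort the single ratio less. These runs show the mechanism, not the size in this trial.

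**The case against.** The strongest reply is that the sentence can be read as ordinary good practice. It does not say that treatment is the term being checked. If age, baseline health status or site violates proportionality, stratifying on it is the standard answer, and Scenario B confirms that it works. It could also help where an apparent treatment violation comes from an omitted prognostic factor. The Kaplan-Meier curves would let a reader see an effect that changes over time. The SAP of 29SEP2023 may define the strata, the diagnostic and an alternative. All of this stands, and it limits the point to the case of a non-proportional treatment effect. It does not rescue the rule in that case: Section 12.7.2 offers nothing else, and curves displayed beside a single ratio do not replace it as the comparison.

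A reader might go further and infer that the reported hazard ratios will be misleading for all four endpoints. The documents do not support that. They give no hazards, nothing shows that the treatment effect is non-proportional, and Section 12.7.2 does not mention a hazard ratio; that one will be reported is inferred from the choice of model.

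**Conclusion.** The point holds in a limited form. As written, the rule corrects non-proportionality of a stratifying covariate and leaves a non-proportional treatment effect uncorrected. That follows from the form of the model and does not depend on the simulations. The size of any distortion cannot be stated; the simulated figures rest on assumed hazards that cross at Day 7.

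The practical reach is time to recovery and time to aggravation. The primary analysis compares proportions and is untouched. The conclusion that no alternative is planned rests on the protocol and the addendum alone. The change is worth making because it is cheap, but it does not bear on the trial's main conclusion.

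**What to change.** In Section 12.7.2 and the matching SAP text:

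- Limit stratified Cox regression to baseline covariates found to be non-proportional. Name the candidate strata and the diagnostic, and state that proportionality of treatment is examined separately.
- For time to recovery and time to aggravation, report the between-arm difference in restricted mean time to Day 60, ∫₀⁶⁰ [S_LAU-7b(t) − S_placebo(t)] dt, with a 95% confidence interval, beside the Cox result and the Kaplan-Meier curves. Report it whatever the proportional-hazards test shows, so that the choice of summary does not depend on the data.
- For time to recovery, count deaths as not recovered through Day 60.
- Do not rely on a log-rank test as the remedy. It is essentially the score test of the same Cox model and adds little here.

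Because results were released on 14MAR2024, label this a supplementary post hoc analysis beside the planned Cox result, unless the SAP of 29SEP2023 already specifies it. The cost is a few sentences and one additional supplementary analysis per endpoint.
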